8.0 DRUG FORMULATION AND PROCUREMENT

8.1 Temozolomide

8.1.1 Other Names

Temodar®, TMZ, Temodal®, methazolastone

8.1.2 Classification – type of agent

Temozolomide is a cytotoxic alkalyting agent.

8.1.3 Mode of Action

Temozolomide is not directly active but undergoes rapid non-enzymatic conversion at physiologic pH to the reactive compound MTIC. The cytotoxicity of MTIC is thought to be primarily due to alkylation of DNA. Alkylation (methylation) occurs mainly at the O6 and N7 positions at guanine.

8.1.4 Storage and Stability

Temozolomide capsules are packaged in amber glass bottles and should be stored at 25°C (temperature excursions between 15-30°C are permitted). Refer to the product label for storage and stability information.

8.1.5 Protocol Dose

The starting dose for the phase I portion of this trial will be 150 mg/m² taken orally on days 1-7 and 15-21 of each cycle (1 cycle = 28 days). The dose will be escalated (or de-escalated) according to the toxicities observed in each cohort of patients. The MTD, once determined in the phase I portion, will be the recommended dose for the phase II portion of the trial. The MTD has been identified at dose level -2: Temozolomide 75 mg/m² per day p.o. days 1-7 and 15-21. As of 12.15.15, all patients moving forward will be treated at this dose.

8.1.6 Preparation

Temozolomide is supplied in white opaque, preservative-free capsules in a variety of dosage strengths.

8.1.7 Protocol Administration

Temozolomide will be administered orally on days 1-7 and 15-21 of each 28-day cycle. Capsules should be swallowed whole with a glass of water. Absorption is affected by food. Temozolomide may be administered on an empty stomach or at bedtime to reduce nausea and vomiting. A dose should not be repeated if vomiting occurs after administration. Capsules should not be opened or chewed. Contact with skin should be avoided if capsules are accidentally opened or damaged.

8.1.8 Incompatibilities

Administration of valproic acid decreases oral clearance of temozolomide by about 5%. The clinical implication of this effect is not known.

8.1.9 Availability

Temozolomide is FDA-approved for the treatment of anaplastic astrocytoma and GBM. Locally-obtained, commercial supplies of temozolomide will be prescribed for this study.

8.1.10 Side Effects

The most common grade 3 or 4 toxicities reported with standard dosing include:

- 8.1.10.1** Lymphopenia < 5%
- 8.1.10.2** Thrombocytopenia < 5%
- 8.1.10.3** Nausea/vomiting < 10%
- 8.1.10.4** Elevated liver enzymes < 10%
- 8.1.10.5** Elevated BUN/Cr < 10%
- 8.1.10.6** Constipation < 10%
- 8.1.10.7** Rash 5%
- 8.1.10.8** Headache < 5%
- 8.1.10.9** Alopecia < 5%
- 8.1.10.10** Lethargy < 1%

8.1.11 Nursing Implications

- 8.1.11.1** Monitor CBC carefully and report any significant changes to the treating physician. Instruct patients to report signs/symptoms of infection, unusual bruising and bleeding to health care team.
- 8.1.11.2** Instruct patients to report any fever, cough, chest pain, or other signs of infection to the health care team.
- 8.1.11.3** Advise patients that a mild-moderate rash may be experienced.
- 8.1.11.4** Work with patients in energy conserving lifestyle methods to combat fatigue.
- 8.1.11.5** Encourage patients to increase fluid intake. Administer stool softeners or laxatives as ordered and monitor for their effectiveness.

8.2 Pazopanib

8.2.1 Other Names

None

8.2.2 Classification – type of agent

Pazopanib is an ATP-competitive tyrosine kinase inhibitor of VEGFR.

8.2.3 Mode of Action

Pazopanib is an orally-bioavailable, ATP-competitive tyrosine kinase inhibitor of VEGFR (-1, -2, and -3), PDGFR (- α and - β) –Kit.

8.2.4 Storage and Stability

Keep in tightly closed containers or packages away from moisture and away from sources of ignition. Avoid direct sunlight.

8.2.5 Protocol Dose

The starting dose for the phase I portion of this trial was 400 mg taken orally on a daily basis for each cycle (1 cycle = 28 days). The dose was escalated (or de-escalated) according to the toxicities observed in each cohort of patients. The MTD has been identified at dose level -2; Pazopanib 400 mg per day p.o. days 1-28.

As of 12.15.15, all patients moving forward will be treated at this dose.

8.2.6 Preparation

For clinical supply, Pazopanib is supplied as a series of aqueous film-coated tablets containing 200 mg or 400 mg of the freebase:

8.2.6.1 200 mg, oval-shaped, white, packaged in bottles containing 34 tablets each

8.2.6.2 400 mg, oval-shaped, white, packaged in bottles containing 68 tablets each.

For commercial supply,

8.2.6.3 200mg, gray, oblong-shaped tablets, packaged in bottles containing 120 tablets each.

Votrient (Pazopanib) commercial available supply with auxiliary label will also be provided by Novartis. The study drug should be administrated and stored according to the instructions specified on the drug labels.

(Note: Sites will start using the commercial supply when they finish the previous clinical supply).

8.2.7 Protocol Administration

Pazopanib should be taken orally without food at least 1 hour before or 2 hours after a meal. The tablets should be swallowed whole and must not be crushed or broken. The time of day the tablets are taken should be relatively constant. If a dose is missed, the patient should take the dose as soon as possible, but not if there are less than 12 hours before the next dose is due. If the next dose is due in less than 12 hours, the patient should skip the missed dose and take the next dose as scheduled. If vomiting occurs after taking pazopanib another dose is not permitted on that day. The patient should resume taking pazopanib at the next scheduled dose. If vomiting persists, the subject should be instructed to notify the investigator.

8.2.8 Incompatibilities

Results from drug-drug interaction studies conducted in cancer patients suggest that pazopanib is a weak inhibitor of CYP3A4, CYP2C8, and CYP2D2 in vivo, but had no effect on CYP1A2, CYP2C9, or CYP2C19.

The concomitant use of strong CYP3A4 inhibitors (e.g., ketoconazole, ritonavir, clarithromycin) may increase pazopanib concentrations and should be avoided. Grapefruit juice should be avoided as it inhibits CYP3A4 activity and may also increase plasma concentrations of pazopanib. A list of CYP3A4 inhibitors is provided in Appendix II.

The concomitant use of strong CYP3A4 inducers (e.g., rifampin) may decrease pazopanib concentrations and should be avoided. Pazopanib should not be used in patients who cannot avoid chronic use of strong CYP3A4 inducers. A list of CYP3A4 inducers is provided in Appendix II.

Concomitant use of pazopanib with agents with narrow therapeutic windows that are metabolized by CYP3A4, CYP2D6, or CYP2C8 is not recommended. A list of these agents is provided in the Appendix II.

Concomitant use of pazopanib and simvastatin (Zocor) increases the risk of ALT elevations and should be undertaken with caution and close monitoring. If a subject receiving concomitant simvastatin develops ALT elevations, follow the Guidelines for Management of Treatment Emergent Hepatotoxicity and discontinue simvastatin. Insufficient data are available to assess the risk of concomitant administration of alternative statins and pazopanib.

Please refer to the development core safety information in the current Investigator's Brochure for detailed information about interactions with simvastatin, CYP3A4 inhibitors, impact on drugs eliminated through UGT1A1 and OATP1B1, and the use of pazopanib with drugs known to increase the gastric pH. Please also refer to Appendix II of this protocol.

8.2.9 Availability

Votrient (Pazopanib) commercial available supply with auxiliary label will be provided by Novartis. The study drug should be administrated and stored according to the instructions specified on the drug label.

Pazopanib will be provided by study supporters Novartis and NCCN. All requests for study drug should be submitted via email to [name] ([contact]), [name] ([contact]), and [name] ([contact]) and should include the following information:

8.2.9.1 Quantities needed

8.2.9.2 Protocol number

8.2.9.3 PI's name and shipping address

8.2.10 Side Effects

8.2.10.1 Very common (≥ 1 in 10): anorexia, headache,

hypertension, diarrhea, nausea, vomiting, abdominal pain, increases in ALT, AST, hair depigmentation, fatigue, asthenia.

8.2.10.2 Common (≥ 1 in 100 and < 1 in 10): thrombocytopenia, neutropenia, hypothyroidism, decreased weight, dysgeusia, transient ischemic attack, myocardial ischemia, QT prolongation, epistaxis, hematuria, dyspepsia, hepatic function abnormalities, hyperbilirubinemia, rash, alopecia, skin depigmentation, Palmar-plantar erythrodysaesthesia syndrome, proteinuria, chest pain

8.2.10.3 Uncommon (≥ 1 in 1000 and < 1 in 100): ischemic stroke, Torsade de Pointes, atrial fibrillation, pulmonary hemorrhage, GI hemorrhage, cerebral hemorrhage, GI perforation, GI fistula

(Note: please refer to updated IB version 14 dated 01.07.16 for more information.)

8.2.11 Nursing Implications

8.2.11.1 Take without food.

8.2.11.2 Monitor liver function tests at baseline while on treatment.

8.2.11.3 Monitor blood pressure.

9.0 STATISTICAL CONSIDERATIONS

The study design is a phase I/II, open-label, non-randomized dose-escalation study to determine the MTD, safety profile, pharmacokinetics, response rate, and overall survival with the combination of temozolamide and pazopanib in patients with advanced pancreatic neuroendocrine tumor.

The MTD determined in phase I will be the recommended Phase II dose. Once the MTD is determined, the study will proceed to a single-arm, open-label Phase II to evaluate efficacy endpoints. Data will be pooled from patients enrolled at both study sites.

9.1 Phase I Endpoints

The primary endpoint in Phase I is MTD and RP2D determination for the combination of temozolamide and pazopanib in patients with advanced pancreatic neuroendocrine tumor. This will be achieved using a standard “3+3” dose escalation as detailed in Section 5.2. Secondary endpoints in Phase I include determining the safety and toxicity profile of the combination of temozolamide and pazopanib, describing the pharmacokinetics, and observing the ORR. Patients who are removed from study for reasons other than disease progression (i.e. for toxicity or patient preference) will be censored for measurement of secondary endpoints at the time of their latest objective tumor assessment.

9.1.1 Sample Size of Phase I

Between 9 and 12 patients will be accrued in phase I. The MTD of the regimen will be determined using standard “3+3” phase I methodology.

9.1.2 Phase I Statistics

Safety will be assessed through a summary of adverse events and laboratory test results. Safety analyses will include all patients who receive at least one dose of study regimen. Verbatim description of treatment-related adverse events will be mapped to thesaurus terms. Adverse events assessed as related to study drug and serious adverse events will be summarized similarly. Adverse events leading to treatment discontinuation will also be summarized. The safety analysis will include a tabulation of all toxicities by grade. The frequency of toxicities will be tabulated separately for each treatment dose level. Treatment safety and toxicity will be evaluated using NCI CTCAE v 4.0 with scheduled assessments every week for the first cycle and then biweekly thereafter.

The statistical analysis for the secondary objectives of phase I will be descriptive in nature. The pharmacokinetics of temozolomide alone (Cycle 1 Day 1) and in combination with pazopanib (Cycle 1 Day 2) will be described in a population of 6 patients enrolled at the MTD. C_{max} and T_{max} will be taken as the observed values. At a minimum, for temozolomide, the following PK parameters will be determined: maximal serum concentration (C_{max}); observed time to achieve C_{max} (T_{max}); minimum (trough) serum concentration (C_{min}); elimination half-life ($t_{1/2}$); elimination clearance (CL_E); volume of distribution at steady-state (V_{ss}), and area under the concentration-time curve extrapolated to infinity (AUC_{inf}). These parameters will be summarized for each person and each day, and each constant will be compared between Day 1 and Day 2 using a Wilcoxon signed rank test. The plasma temozolomide concentration versus time relationships will be modeled using the SAAM II software system. The 6 patients enrolled at the MTD to form the PK cohort will be included in the phase II analysis for all other endpoints.

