5.2 Study Drug Administration

Both study drugs will be orally self-administered. Patients will be provided a drug diary to record the date and time of each dose of temozolomide and pazopanib, as well as any skipped doses or doses intentionally held per the treating physician's instructions. The study team will instruct patients on completing the diary, and will collect the completed diaries for the previous cycle on Day 1 of the subsequent cycle.

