5.2.1 Temozolomide

Patients will be instructed to take temozolomide orally once a day starting on Cycle 1 Day 1 of treatment. The dose of temozolomide will depend on the phase and cohort onto which the patient is enrolled (refer to Section 5.3 for dose escalation rules). For phase I, the starting dose of temozolomide will be 150 mg/m² per day. Patients will continue temozolomide for 7 consecutive days at a time, every other week (Days 1-7 and 15-21 of the cycle). One cycle equals 28 days. Patients will continue to take temozolomide every other week until study discontinuation (refer to Section 5.8 for duration of treatment and discontinuation rules).

Temozolomide tablets will be swallowed whole. Patients will be instructed to fast at least 1 hour before and 1 hour after administration of temozolomide. Water is allowed during the fasting period.

Temozolomide may be taken before or after pazopanib (on days when both drugs are taken), but it is recommended that they be taken around the same time. If a dose is missed, the patient should take the dose as soon as possible, but only if there are 12 or more hours remaining before the next dose is due. If the next dose is due in less than 12 hours, the subject should skip the missed dose and take the next dose as scheduled.

If vomiting occurs after taking temozolomide, the patient should not take a replacement dose on that day. The patient should resume taking temozolomide at the next scheduled dose on the following day.

(Note: For patients in the PK cohort, please refer to the Study Parameters Table for PK Cohort for information regarding temozolomide doses on Cycle 1, Days 1-3.)

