5.2.2 Pazopanib

Patients will be instructed to take pazopanib orally once a day starting on Cycle 1 Day 1 of study treatment. The dose of pazopanib will depend on the phase and cohort onto which the patient is enrolled (refer to Section 5.3 for dose escalation rules). For phase I, the starting dose of pazopanib will be 400 mg per day. Pazopanib will be taken daily continuously study discontinuation (refer to Section 5.8 for duration of treatment and discontinuation rules).

Pazopanib should be taken orally without food at least 1 hour before or 2 hours after a meal. The tablets should be swallowed whole and must not be crushed or broken. The time of day the tablets are taken should be relatively constant. Pazopanib may be taken before or after temozolomide (on days when both drugs are taken), but it is recommended that they be taken around the same time. If a dose is missed, the patient should take the dose as soon as possible, but only if there are 12 or more hours remaining before the next dose is due. If the next dose is due in less than 12 hours, the subject should skip the missed dose and take the next dose as scheduled.

If vomiting occurs after taking pazopanib, the patient should not take a replacement dose on that day. The patient should resume taking pazopanib at the next scheduled dose on the following day. If vomiting persists, the patient should be instructed to notify the investigator.

(Note: For patients in the PK cohort, please refer to the Study Parameters Table for PK Cohort for information regarding pazopanib doses on Cycle 1, Days 1-3.)

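### Oral dosing can give only apparent clearance and volume, yet Section 9.1.2 names elimination clearance and V_ss, and the PK sections do not match fasting on the two days compared

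*Combined protocol and SAP*

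**What the plan says.** Section 9.1.2 describes the phase I secondary analyses as descriptive. It lists the temozolomide parameters to be determined as a minimum: Cmax, Tmax, Cmin, half-life, elimination clearance (CL_E), "volume of distribution at steady-state" and AUC to infinity. It then adds that "each constant will be compared between Day 1 and Day 2 using a Wilcoxon signed rank test". The pharmacokinetics "will be described in a population of 6 patients enrolled at the MTD". Section 6.1.2.2 gives the purpose, which is to examine what pazopanib does to temozolomide pharmacokinetics.

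On route, Section 5.2 says: "Both study drugs will be orally self-administered". No intravenous dose and no value of F appears.

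On food, Section 8.1.7 says of temozolomide: "Absorption is affected by food". Section 5.2.1 says: "Patients will be instructed to fast at least 1 hour before and 1 hour after administration of temozolomide". Section 5.2.2 says: "Pazopanib should be taken orally without food at least 1 hour before or 2 hours after a meal". Both sections recommend, but do not require, taking the two drugs at about the same time. Section 12.1.1.1 holds pazopanib on Day 1. Neither Section 6.1.2.2 nor Section 12.1.1 sets a fasting interval or meal condition common to the two days.

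**The concern.** The Day 1 to Day 2 comparison is the trial's only evidence on a drug interaction. A quantity named elimination clearance invites the reader to take a difference between days as an effect on elimination. That reading would bear on the argument in Section 1.5.5 that interaction through metabolism is unlikely. With oral data alone, a difference in the amount absorbed produces the same result.

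The fasting rules make this more than a labelling point. Any difference in fasting that they allow lies between the day without pazopanib and the day with it. If patients used that latitude in the same way, the effect would not average out across the 6. It would also enter Cmax, Tmax and AUC.

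**Working it through.** The plan states no effect size, variability or power for this comparison, so there is no figure to reproduce. The F ratios, within-patient CVs and model constants below are assumptions. The documents give no size for the food effect and do not say whether it concerns rate or extent.

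**Step 1: what oral data identify.** After an oral dose, AUCinf = F × Dose / CL, so Dose / AUCinf = CL/F. Volume is likewise V/F. Half-life = ln 2 × V/CL, in which F cancels. Compartmental modelling in SAAM II does not change this: F must be fixed at some value, and the plan states none.

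**Step 2: change in extent only.** Let R be the Day 2 to Day 1 ratio of F, with true CL and V the same on both days. The relative change in CL/F and in V/F is 1/R - 1, and in AUC it is R - 1.

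| R | CL/F and V/F | AUC | Half-life |
|---|---|---|---|
| 0.7 | 1/0.7 - 1 = +43% | -30% | 0% |
| 0.8 | 1/0.8 - 1 = +25% | -20% | 0% |
| 1.2 | 1/1.2 - 1 = -17% | +20% | 0% |
| 1.3 | 1/1.3 - 1 = -23% | +30% | 0% |

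**Step 3: change in rate only.** Take a one-compartment oral model with CL = 1, V = 3 (arbitrary units) and F unchanged, and let the absorption rate constant ka fall from 3 to 1.5 or to 1.
- CL/F does not change.
- Cmax falls by 14% or 24%, and Tmax rises by 57% or 100%.
- A volume computed as CL × mean residence time, without subtracting absorption time, equals CL × (V/CL + 1/ka). It goes from 3.33 to 3.67 (+10%) or to 4.00 (+20%).

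**Step 4: could such a shift reach nominal significance with 6 patients?** The smallest two-sided signed rank p-value is 2/2^6 = 0.031 and the next is 4/2^6 = 0.0625. At an assumed 0.05 level, all 6 differences must therefore have the same sign. Suppose R = 0.8 in every patient. The mean log difference is -ln 0.8 = 0.223, with SD = √2 × √ln(1 + CV²), and the probability is about Φ(0.223/SD)^6.
- CV 5%: SD 0.071, probability above 0.99.
- CV 10%: SD 0.141, probability 0.70.
- CV 20%: SD 0.280, probability 0.24.

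**Step 5: what the fasting rules allow.**

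| | Day 1 | Day 2 |
|---|---|---|
| Drugs | Temozolomide | Temozolomide and pazopanib |
| Temozolomide minimum | 1 h before and 1 h after | The same |
| Pazopanib rule | Not in play | At least 1 h before, or 2 h after, a meal |

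A patient dosed 1 hour after breakfast on Day 1, and with both drugs 2 hours after breakfast on Day 2, complies. So does a patient with the same overnight fast on both days.

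**Step 6: Day 2 time zero.** Section 6.1.2.2 places the time-zero sample before both drugs. Section 12.1.1.2 has patients continue temozolomide as instructed and ties only pazopanib to the clinic sample. If temozolomide were taken before that sample, the Day 2 times would not be times after the temozolomide dose, and Cmax, Tmax and AUC would be affected directly.

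**The case against.** The strongest reply is that the plan makes no mechanistic claim. The analysis is called descriptive, the objective in Section 2.1.2.2 is to describe, and an experienced reader will take clearance and volume from oral data as apparent values. Half-life, Tmax and AUC are already among the planned outputs. This largely stands. A reader might infer that the plan commits the sponsor to reporting an absorption change as an elimination effect, and the text does not go that far. What remains is that the named quantities cannot be determined, each is put to a formal test, and no sentence says how to read them.

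On fasting, the same temozolomide minimum applies on both days. A reader might infer that Day 2 always demands a 2-hour fast. It does not: the 2-hour limit concerns a dose that follows a meal, and simultaneous dosing is only recommended. Clinic dosing and the shared 24-hour sample also keep clock times close. Nothing shows that patients will eat 1 to 2 hours before the Day 1 dose, or that such a difference would change F by 20% or 30%. Sections 5.2.1 and 5.2.2 also point to a separate parameters table for the PK cohort, and Section 12.1.4 to a laboratory manual. Neither is among the documents reviewed, so the absence of a common fast is established only for the sections available.

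A reader might also want to treat parallel shifts in CL/F and V/F with unchanged half-life as proof of an absorption change. That is unsound. Half-life is proportional to V/CL, so a real change that moves CL and V together, for example through the unbound fraction, leaves it unchanged too.

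**Conclusion.** The point holds as one of identifiability and interpretation. Section 9.1.2 names two parameters that oral data cannot supply; only CL/F and V/F can be estimated. With elimination unchanged, assumed F ratios of 0.7 to 1.3 would shift both by +43% to -23%. A change in absorption rate alone would leave CL/F where it is. Unequal fasting is permitted rather than prescribed, and the documents give neither the size of the food effect nor whether it concerns extent, so they do not show that a bias of this size will occur. The case for matching the two days is that the permitted difference coincides with the comparison and is almost free to remove.

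The consequence is confined to the interaction result, a phase I secondary objective in 6 patients. The MTD rests on DLTs and the phase II decision on response rate. The change should be made, but it is not critical to the trial.

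**What to change.** 1. In Section 9.1.2, rename the parameters apparent clearance (CL/F) and apparent volume (V/F). State that a Day 1 to Day 2 difference in either cannot by itself be attributed to elimination, and that it will be read descriptively together with half-life, Tmax and AUC.
2. In Section 12.1.1, require the same pre-dose fasting and meal conditions on both PK days, within the limits already in Sections 5.2.1 and 5.2.2, and record actual meal and dose times.
3. Reconcile Section 12.1.1.2 with Section 6.1.2.2 on whether Day 2 temozolomide is taken after the time-zero sample.

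The cost is a few sentences, slightly tighter meal instructions for 6 patients on two days, and a more modest claim. No samples, visits or patients are added. Even with matched fasting, CL and F cannot be separated from oral data, so the interpretation statement is needed in any case. If PK sampling is already complete, the relabelling and that statement still apply.
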